9.3.2 Pharmacokinetic endpoints

Pharmacokinetic endpoints will include evaluation in plasma of the following parameters: C_{\max} , t_{\max} , AUC, $AUC_{(0-\text{last})}$, $t_{1/2}$, CL, and V_{ss} .

9.3.2.1 Pharmacokinetic sampling time

Pharmacokinetic sampling will occur during the PAP and ETP according to the time points provided in [Section 1.2](#). During the study period, for the switch from Process C(■) IMP to the updated manufacturing process C(■) IMP, samples for PK will be collected at the second dose that is administered after the switch following the same schedule in [Section 1.2.3](#). If a patient receives only a partial infusion (eg, due to a safety concern), then sampling will be repeated at the next infusion of study drug.

Time windows for PK sampling are ± 10 minutes for collection times < 8 hours after the end of infusion and ± 3 hours for collection times ≥ 8 hours after the end of infusion. Blood will be drawn using an indwelling catheter from an arm that was not used for study drug administration. The exact time/date of PK sampling, study drug administration (including infusion start and stop times), and infusion rate will be recorded.

9.3.2.2 Pharmacokinetic handling procedures

Procedures for collection, storage, and shipment of PK samples are provided in the laboratory manual.

9.3.2.3 Bioanalytical methods

Concentrations of olipudase alfa in plasma will be determined using a validated enzyme-linked immunosorbent assay method.

9.3.2.4 Pharmacokinetic parameters

The pharmacokinetic parameters listed in [Table 2](#) will be calculated from single- and multiple-dose data, as appropriate, and analyzed by non-compartmental methods.

Table 2 - Pharmacokinetic parameters and definitions

Parameter	Parameter definition
C_{max}	Maximum plasma concentration observed
t_{max}	Time to reach C_{max}
AUC_{0-last}	Area under the plasma concentration versus time curve calculated using the trapezoidal method from time zero to the real time
AUC	Area under the plasma concentration versus time curve extrapolated to infinity according to the equation: $AUC = AUC_{last} + \frac{C_{last}}{\lambda_z}$. Values with a percentage of extrapolation >20% will not be taken into account in the descriptive statistics.
$t_{1/2z}$	Terminal half-life associated with the terminal slope (λ_z) determined according to the following equation: $t_{1/2z} = \frac{0.693}{\lambda_z}$, where λ_z is the slope of the regression line of the terminal phase of the plasma concentration versus time curve, in semi-logarithmic scale. Half-life is calculated by taking the regression of at least 3 points.
CL	Total body clearance of a drug from the plasma calculated using the equation $CL = \frac{Dose}{AUC}$
V_{ss}	Volume of distribution at steady state using the equation $V_{ss} = \frac{CL \times AUMC}{AUC}$

The analyte and matrix for all PK parameters are olipudase alfa and plasma, respectively.

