8.1.2 Route and method of administration

Duration of study drug infusions will be the same regardless of treatment assignment and each infusion will last for approximately 220 minutes, except at W0 when it will last approximately 35 minutes and at W54 where it will last approximately 255 minutes.

For each patient, intravenous infusion with study drug should occur at approximately the same time of day. There are no restrictions on the infusion timing with respect to meals.

See [Section 8.1.3.2](#) for information on dose adjustments following dosing delays or missed infusions.

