4. Remove “of different doses.”

In section(s): Clinical trial summary (Study objectives, Primary objective), 5.1

Rationale: The 1.0 mg arm is no longer part of the study

5. Change randomization ratio from 2:1:2 to 1:1 during the PAP.

In section(s): Clinical trial summary (Statistical considerations [sample size determination]), 6.1, 8.4, 11.2

Rationale: Removing the 1 mg/kg arm in the PAP resulted in a necessary change in the randomization to 1:1. During the 4 year ETP, all patients will receive olipudase alfa.

6. Add inclusion criterion for mean splenomegaly-related symptoms score

In section(s): Clinical trial summary (Study population [Inclusion criteria]), 7.1

Rationale: To increase the statistical power of the evaluation of the secondary endpoint, “Change in splenomegaly-related symptom score from baseline to week 52”.

7. Add contraception requirements following the last olipudase alfa infusion.

In section(s): Clinical trial summary (Study population, Main selection criteria, Inclusion criteria), 7.1, 10.3

Rationale: Conventionally, true abstinence or contraception is required during the treatment period and following the last administration for at least 5 multiples of the investigational product’s half-life. Based upon the 24-hour half-life of olipudase alfa, the minimum duration for requiring contraception use is 5 days following the last infusion. To be conservative, the period of time that each patient will be required to either practice true abstinence or use 2 acceptable, effective methods of contraception was expanded to include 15 days after the patient’s last olipudase alfa infusion.

8. Clarify that the longest study duration per patient will be for at least 3 years and up to 5 years and 3 months dependent upon continued regulatory approval of the protocol.

In section(s): Clinical trial summary (Duration of study period [per patient]), 6.2.1

Rationale: Previous text can be interpreted as allowing patients to be in the study for only 3 years, so clarification was added.

9. Changed interim analysis wording from “interim analysis may be conducted” to “no interim analysis is planned.”

In section(s): Clinical trial summary (Statistical considerations, Interim analysis), 6.3

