### 2.1.6 Pharmacokinetic variables

Pharmacokinetic endpoints will include evaluation in plasma of the following parameters:  $C_{max}$ ,  $AUC_{0-\tau}$ ,  $AUC_{0-last}$ ,  $t_{1/2}$ , CL, and  $V_{\beta}$ . Definition of each parameter is provided in Section 9.3.2.4 of the study protocol. The process of sample collection has been outlined in Section 9.3.2.1.

Concentrations of olipudase alfa in plasma will be determined using a validated enzyme-linked immunosorbent assay method.

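### Protocol Table 2 defines Vss by a bolus equation, although every PK-sampled dose is an infusion of about 220 or 255 minutes; applied as written it overstates Vss, by about 5% if MRT is about 35 h

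*Protocol*

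**What the plan says.** Protocol Section 9.3.2.4, Table 2, lists Vss ("Volume of distribution at steady state using the equation") with the formula Vss = CL x AUMC/AUC. The same table gives CL ("Total body clearance of a drug from the plasma calculated using the equation") as Dose/AUC. It defines neither AUMC nor time zero, and it contains no term for infusion duration. The stated method is non-compartmental (Protocol Sections 9.3.2.4 and 11.5.6.1).

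The SAP gives no Vss formula of its own. Section 2.1.6 sends the reader back to the protocol: "Definition of each parameter is provided in Section 9.3.2.4 of the study protocol".

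On infusion length, Protocol Section 8.1.2 says that "each infusion will last for approximately 220 minutes", with two exceptions: "except at W0 when it will last approximately 35 minutes" and "at W54 where it will last approximately 255 minutes". Protocol Section 1.2.3 schedules PK profiles at Weeks 2, 10, 14, 26, 38, 52, 54, 68, 80, 132, 184 and 236, so the one short infusion, at Week 0, is never sampled.

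Protocol Section 9.3.2.1 requires the infusion start and stop times and the infusion rate to be recorded.

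**The concern.** CL x AUMC/AUC gives Vss only when the whole dose enters at time zero. When drug enters over several hours, AUMC/AUC also contains the average time that drug spends waiting to enter. If that time is not subtracted, it is counted as residence in the body and Vss comes out too high.

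Vss is a named PK endpoint (Protocol Section 9.3.2), and its written definition does not fit any dose at which it will be calculated. The error always has the same sign. It also depends on how the drug was delivered, so a patient whose infusion was slowed carries a larger error than one whose infusion was not. Protocol Section 11.5.6.1 plans to look at PK parameters over time and in relation to immunogenicity, where an artefact of infusion length would be unwelcome.

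**Working it through.** The documents state no Vss value, MRT or bias, so there is no plan figure to reproduce.

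**Inputs**
- Infusion duration T: 220 minutes, or 255 at Week 54 (Protocol Section 8.1.2).
- Half-life: 24 h. It appears only in a contraception rationale in Protocol Appendix C, under Amendments 07 and 05-GB: "Based upon the 24-hour half-life of olipudase alfa, the minimum duration for requiring contraception use is 5 days following the last infusion". That use is consistent with itself, since 5 x 24 h = 5 days.
- MRT: not given. It is an assumption below.

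**Formula**
1. With linear kinetics and time zero at the start of drug infusion, mean times add: AUMC/AUC = MRT + MIT.
2. For a single uninterrupted constant-rate infusion, MIT = T/2.
3. True Vss = CL x MRT. The printed equation returns CL x (MRT + MIT), so the relative overstatement is MIT/MRT.
4. The timing of input does not change total AUC, so CL = Dose/AUC is unaffected.

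**One compartment, 24 h half-life**
- MRT = 24/ln 2 = 34.62 h.
- 220 minutes: MIT = 220/120 = 1.833 h, and 1.833/34.62 = 5.3%.
- 255 minutes, if drug enters evenly throughout: MIT = 255/120 = 2.125 h, and 2.125/34.62 = 6.1%.
- Numerical integration of the infusion profiles gave the same values (5.29% and 6.14%).
- Carry-over is negligible: doses are 14 days apart, which is 14 half-lives.

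**Sensitivity to the assumed MRT, 220 minutes**

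| Assumption | MRT (h) | Overstatement |
|---|---|---|
| One compartment, half-life 36 h | 51.9 | 3.5% |
| One compartment, half-life 24 h | 34.6 | 5.3% |
| Two compartments, 90% of AUC in the terminal phase | 31.6 | 5.8% |
| Two compartments, 70% | 25.5 | 7.2% |
| Two compartments, 55% | 21.0 | 8.7% |
| MRT needed for 9% | 20.4 | 9.0% |

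The two-compartment rows assume a 24 h terminal and a 3 h initial half-life; the 3 h figure is not in the documents. If 24 h is the terminal half-life and there is a distribution phase, MRT falls below 34.6 h, so 5.3% is the low end on that reading.

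**Sensitivity to how drug is delivered at Week 54, MRT 34.6 h**

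255 = 220 + 35, which may mean a two-part infusion. That is an inference; the documents do not say it.

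| Where the drug is | MIT (min) | Overstatement |
|---|---|---|
| First 35 minutes only | 17.5 | 0.8% |
| First 220 minutes | 110 | 5.3% |
| Evenly over 255 minutes | 127.5 | 6.1% |
| Last 220 minutes | 145 | 7.0% |

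**Slowed infusion.** Protocol Section 8.8 allows the rate to be cut, for example by half. A whole infusion at half rate lasts 440 minutes, so MIT = 220 minutes = 3.667 h, and 3.667/34.62 = 10.6%.

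**The case against.** **Literal use is not certain.** Protocol Section 11.5.6.1 and SAP Section 2.4.7.2 allow nonlinear mixed-effects modelling, which would not use this equation, and PK software may apply an infusion correction itself. This stands as a limit on the claim. But non-compartmental analysis is the stated method, and if software did correct silently, the reported Vss would no longer match its written definition.

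**The impact is small.** No hypothesis test is planned on Vss; it is only summarised descriptively. A roughly common offset largely cancels between 220-minute visits. This stands.

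**The SAP link is imperfect.** In the text available for this review, the symbol in SAP Section 2.1.6 does not read as Vss. The SAP abbreviation list defines Vss, so this is probably a text-extraction fault, and nothing rests on it.

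**Stronger readings that the documents do not support.**
- A reader might take 5% to 9% as established. Only 5.3% follows from a documented half-life, and then only with one compartment. The upper end needs an MRT of about 20 h, which appears nowhere.
- A reader might infer that Week 54 must be more inflated than Week 52, creating a false difference between visits. That needs drug to run evenly over all 255 minutes. Former placebo patients begin true escalation at Week 54 while active patients have a mock crossover, and the documents do not say which part of the infusion carries drug. The Week 54 error could be smaller than at Week 52.
- A reader might conclude that subtracting T/2 is always right. It is exact only for one uninterrupted constant-rate infusion. Protocol Section 8.8 foresees rate reductions and interruptions, and SAP Section 2.4.4.1 sums volume over several infusions within a visit. If Week 54 drug were confined to the first 35 minutes, subtracting 127.5 instead of 17.5 minutes would give (17.5 - 127.5)/60/34.62 = -5.3%, as large as the error being removed.

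**Conclusion.** The point holds as a definitional error of modest consequence. The printed Vss equation is the bolus form and does not apply to any PK-sampled dose in this study. Used as written, with time zero at the start of infusion, it overstates Vss by MIT/MRT.

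The best-supported size is about 5.3% at 220 minutes, from the protocol's 24-hour half-life with one compartment. A range of about 5% to 9% corresponds to an assumed MRT of about 35 to 20 h, and values outside it cannot be excluded because the documents give no MRT. For Week 54 the size, and its direction relative to other visits, remain open until the documents say how drug is delivered over the 255 minutes.

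CL, AUC, Cmax and half-life are unaffected, and no efficacy or safety conclusion depends on this.

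**What to change.** Replace the Table 2 equation with Vss = CL x (AUMC/AUC - MIT), and state three things alongside it:
- Time zero is the start of drug infusion.
- AUMC is extrapolated to infinity.
- MIT is the mean input time, calculated from the recorded start and stop times and rates of drug infusion. It equals T/2 when there is one uninterrupted constant-rate infusion of duration T.

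For Week 54, use the times during which drug itself was running, which may differ from the total infusion time.

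SAP Section 2.1.6 can keep its cross-reference once the table is corrected. Alternatively, the equation can be given there and the difference from the protocol listed in SAP Section 1.5.

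The inputs are already collected, so no new samples or visits are needed. Reported Vss becomes slightly lower, and any values already calculated with the printed equation would need recalculating to be comparable. A change to the protocol text goes through the usual approvals in Protocol Section 15, so it can wait for the next amendment.

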9.4 PHARMACOGENETIC ASSESSMENTS

In addition to patients who have blood drawn for the baseline assessment of condition-related genotypes (See [Section 9.6.3](#)), for those patients who signed the optional pharmacogenetic informed consent form, a blood sample will be collected and stored for other pharmacogenetic analyses.

This blood sample will be transferred to a site that will, on behalf of the sponsor, extract DNA from the sample. This sample may be used to determine a possible relationship between genes and response to treatment with olipudase alfa, how the body processes olipudase alfa and possible side effects to olipudase alfa.

This blood sample, and the DNA that is extracted from it, will be assigned a second number, a Genetic ID (deidentification code) that is different from the patient identification (ID). This “double coding” is performed to separate a patient’s medical information and DNA data.

The clinical study data (coded by patient ID) will be stored in the clinical data management system, which is a distinct database in a separate environment from the database containing the

pharmacogenetic data (coded by Genetic ID). The key linking patient ID and Genetic ID will be maintained by a third party, under appropriate access control. The matching of clinical data and pharmacogenetic data, for the purpose of data analysis, will be possible only by using this key, which will be under strict access control. All data will be reported only in coded form in order to maintain confidentiality.

The DNA will be stored for up to 15 years from the completion of the clinical study report, in compliance with applicable country-specific regulations.

Special procedures for storage and shipping of pharmacogenetic samples are described in detail in the laboratory manual.

9.5 FUTURE USE OF SAMPLES

For patients who have consented to it, left over samples following testing may be used for other research purposes (excluding genetic analysis) related to ASMD. These samples will be stored for 15 years after end of the study in compliance with applicable country-specific regulations.

These other research analyses will help to understand either disease subtypes or drug response, or to develop and/or validate a bioassay method, or to identify new drug targets or biomarkers.

These samples will remain labeled with the same identifiers as ones used during the study (ie, subject/patient ID) and will be transferred to a Sanofi site (or a subcontractor site), which may be located outside of the country where the study is conducted. Safeguards for protecting patient confidentiality and personal data have been included (see [Section 14.3](#) and [Section 14.5](#)).

9.6 OTHER ASSESSMENTS

9.6.1 Demographic information and medical history

During patient screening, demographic information including gender, date of birth, and ethnicity will be collected from each patient. Additionally, patients will provide a complete medical history. Specific information relating to any relevant prior or existing medical conditions/surgical procedures will be recorded on the patient's e-CRF. The patient's diagnosis of ASMD and first symptom date will also be collected and recorded, if available.

9.6.2 Acid sphingomyelinase enzyme activity

Acid sphingomyelinase activity will be measured as specified in [Section 1.2](#) in peripheral leukocytes and dried blood spot. A central laboratory may conduct the analysis of the samples and provide reports.

9.6.3 Genotyping: SMPD1, CHIT1, UGT1A1

Genotyping of SMPD1 and uridine diphosphoglucuronosyltransferase 1 family, polypeptide A1 (UGT1A1) mutations will be performed by central laboratories if historical results are not available, or if historical results are available, but mutations were not annotated using the guidelines of the Human Genome Variation Society (<http://www.hgvs.org/>). Genotyping of CHIT1 will be performed by the sponsor if historical results are not available. Mutations will be annotated according to the guidelines of the Human Genome Variation Society (<http://www.hgvs.org/>).

Sample processing, storage, and shipment guidelines are provided in the laboratory manual.

9.7 APPROPRIATENESS OF MEASUREMENTS

Dose escalation is necessary to progressively reduce stores of accumulated sphingomyelin and to avoid a large release of ceramide. Clinical AEs and safety biomarkers identified in the Phase 1 single-dose and repeat-dose studies study will also be used to monitor treated patients for potential DLTs (as described in [Section 8.1.4](#)).

If a patient experiences an IAR suggestive of a hypersensitivity reaction (as defined in [Section 10.4.1.3](#)), blood samples for anti-olipudase alfa antibody (IgG and IgE), tryptase activity, and complement activation testing will be collected. For patients in whom IgG antibodies develop, neutralizing antibody testing will also be performed.

Efficacy parameters include improvements in spleen and liver volume (as measured by abdominal MRI), pulmonary imaging and function (HRCT, X-ray, PFTs), cardiopulmonary function by treadmill ergometry, bone disease infiltration, hematology parameters, and patient-reported health-related quality of life instruments.

The DL_{CO} was chosen as a primary efficacy endpoint because this PFT reflects the underlying pathophysiological infiltration manifested by disease foam cells and changes in DL_{CO} can objectively show the effect of olipudase alfa treatment on lung function and reducing local inflammation. Pulmonary involvement is common and progressive, although the extent and severity of involvement varies widely among patients (21). Foam cell infiltrates of the pulmonary alveoli block oxygen uptake through the alveolar wall into the blood vessels. This abnormal diffusing capacity is consistent with ILD (9) which may manifest with coughing, shortness of breath, and recurrent respiratory infections. With low partial pressure of oxygen (PO₂) values, patients are affected by dyspnea upon exertion. In most patients with ASMD, decreased pulmonary diffusion secondary to alveolar infiltration becomes evident in childhood and progresses with age (22). Life-threatening bronchopneumonia may occur and cor pulmonale has been described; progressive pulmonary involvement is associated with higher morbidity and mortality (21). Severely affected patients may experience significant pulmonary compromise by age 15 to 20 years. The excess sphingomyelin and other lipids resulting from ineffective ASM clearance from macrophages result in secretion of inflammatory cytokines that lead to fibrosis and diminished lung capacity (23). Some patients develop chronic oxygen dependence with progressive pulmonary failure (21).

Changes in health-related quality of life after 52 weeks administration of study drug will be assessed with the instruments listed in [Section 9.1.4.13](#).

Changes from baseline in spleen volume and DL_{CO}, separately, at Week 52 were selected as the primary efficacy endpoints in this Phase 2/3 study. Splenomegaly is a significant, consistently present manifestation of ASMD, and the degree of splenomegaly has been recognized as clinically relevant by disease experts and shown to be positively correlated with liver volume and triglyceride levels, and negatively correlated with white blood cell count, hemoglobin, high density lipoprotein, percent predicted FVC, and height Z score (24). In both ASMD and a similar lysosomal storage disorder, Gaucher disease, splenomegaly is central to the underlying pathophysiology and is usually the first presenting clinical sign. Furthermore, reduction in spleen volume is recognized as a clinically meaningful endpoint in Gaucher disease (25, 26).

Clinical manifestations common to both ASMD and Gaucher disease include hepatosplenomegaly, thrombocytopenia, and anemia. Both diseases primarily affect the monocyte/macrophage lineage of cells and thus are diseases that affect the reticuloendothelial system. The main sphingolipids that accumulate in Gaucher disease (glucosylceramide) and ASMD (sphingomyelin) are major components of the plasma membranes of red blood cells, white blood cells, and platelets, which cannot be broken down by macrophages. Accordingly, assessments have been planned to monitor changes in hematology.

Due to the known association of sphingomyelin with cholesterol, patients with ASMD often accumulate cholesterol, and subsequently are affected by dyslipidemia, characterized by a high atherogenic cardiovascular risk profile. Typically, the dyslipidemia is characterized by low concentrations of HDL and high concentrations of total cholesterol (27, 28) and recent case reports have described the occurrence of premature coronary artery disease (27). Accordingly, the fasting lipid profile will be assessed as an efficacy parameter and the NMR spectrum of HDL will be characterized (12, 13, 29). NMR lipid profiles analyzed for all patients through 52 weeks of treatment were not identified as an informative efficacy biomarker thus will be removed from the protocol after the cutoff date for a planned second database lock of the study for purpose of regulatory submissions in 2021.

Because skeletal involvement can lead to osteopenia or osteoporosis, common manifestations of ASMD and splenomegaly have been shown to be inversely correlated with lumbar spine bone mineral density Z-scores (30), the severity of bone disease will be measured at baseline and once every year. A biomarker for bone resorption, C-telopeptide concentrations in serum have been shown to be decreased in patients with Gaucher disease.

Although hemoglobin level, platelet count, and white blood cell count will comprise part of the standard safety laboratory assessments, these parameters are often abnormal in patients with ASMD because many cells of the reticuloendothelial system originate in the bone marrow and it is one of the most extensively involved organs in ASMD (31, 32). Bone marrow involvement, combined with hypersplenism, contributes to the thrombocytopenia, anemia, and to the neutropenia sometimes observed in patients with ASMD.

Biomarkers will be measured that are known to be associated with macrophage proliferation (ACE), secreted by activated (NP cells) macrophages (chitotriosidase and CCL18), and

inflammatory background triggered in sphingolipidoses (bone-specific alkaline phosphatase, C-telopeptide). Changes in these biomarkers have supported the clinical responses observed with enzyme-replacement and substrate-reduction therapies in other sphingolipidoses such as Gaucher disease Type 1 and Fabry disease (33, 34, 35). The initial objective to monitor ACE changes through 52 weeks of treatment for all patients has been achieved; no further longitudinal analysis is required after the cutoff date for a planned second database lock of the study for purpose of regulatory submissions in 2021. CCL18 and chitotriosidase will continue to be monitored to assess overall disease burden.

